5.3. Study Phases

Screening Phase: Before the first dose of study medication.

Treatment Phase: Between the date of first dose of study medication and the date of the last dose of study medication plus 30 days.

End of Treatment: Date of last dose of study medication plus 30 days. Assessments performed at the “end of treatment visit” will be included in this phase.

Follow-up Phase: After end of treatment until the subject’s completion or withdraw from the study or study closeout.

5.4. Convention of Time Computations

By convention, one month equals to 30.4375 days and one year equals to 365.25 days. Duration in days between 2 time points will be calculated as (end date – start date + 1).

5.5. Baseline Value

The last non-missing value collected on or before the day of randomization.

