Abbreviations: AE=adverse event; ALT= alanine aminotransferase; AML=acute myeloid leukemia; AST= aspartate aminotransferase; β -hCG=beta human chorionic gonadotropin; BP=blood pressure; BUN= blood urea nitrogen; CR= complete response; CRi= complete response with incomplete blood cell count recovery; ECG=electrocardiogram; ECOG=Eastern Cooperative Oncology Group; EOT=end of treatment; EQ=EuroQol; F/U= follow-up; HBV: hepatitis B virus; HR=heart rate; ICF=informed consent form; INR= international normalized ratio; LDH= lactate dehydrogenase; LVEF= left ventricular ejection fraction; MUGA= Multi Gated Acquisition Scan; NK= natural killer (cells); PD=pharmacodynamics(s); PK=pharmacokinetic(s); PRO= patient-reported outcomes; PT= prothrombin time; aPTT= partial thromboplastin time; SAE=serious adverse event; T&E=Time & Events; WBC= white blood cell.						

TIME AND EVENTS SCHEDULE – TABLE 1B [PART B] UP TO AND INCLUDING AMENDMENT 5

Procedure (Part B)	Notes	Screening Phase	Open-Label Treatment Phase		Follow-up Phase
		Within 28 days before randomization	Day 1 of each cycle (\pm 48 hours) unless otherwise indicated (each cycle = 28 days)	EOT	Every 3 months (\pm 7 days)
NOTE: The EOT Visit should occur within 30 days (\pm 7 days) of last dose for subjects. The Follow-up Phase will continue until death, loss to follow-up, consent withdrawal for study participation, or study end, whichever occurs first.					
Screening/Administrative					
Informed consent	ICF must be signed before any study-related procedures	X			
Demography/medical history		X			
Eligibility criteria	Minimum criteria for the availability of documentation supporting the eligibility criteria are described in Section 17.4, Source Documentation. Sponsor review of key eligibility and approval is required prior to randomization. Check clinical status again before first dose of study medication.	X			
Study Drug Administration (for details see also Section 6)					
Randomization	Within 3 days prior to the first dose	X			
Decitabine			Days 1, 2, 3, 4, and 5		
Talacotuzumab	Subjects randomized to Arm 1		Days 8 and 22 (\pm 24 hours)		
Safety Assessments					
Physical examination	Must be assessed within 3 days of Day 1 of each specified cycle, reviewed prior to starting the cycle and changes that are clinically significant must be reported on the AE page	X	X	X	
ECOG performance status evaluation	Must be assessed within 3 days of Day 1 of each specified cycle	X	X	X	

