Medical resource utilization	Information on all health care needs during treatment (eg, physiotherapist) to be collected	Continuous from the time of signing of the ICF until 30 days after the last dose of study drug			
Patient-reported outcomes					
FACT-Leu	PROs should be performed on Day 1 of each cycle before dosing and before any study tests or procedures are conducted.		X	X	Only at first FU
EQ-5D-5L			X	X	Only at first FU
Laboratory Assessments					
Hematology	At least the following parameters (hemoglobin, platelet count, absolute WBC count, absolute monocyte count, absolute basophil count, absolute eosinophil count, absolute neutrophil count, absolute lymphocyte count, and peripheral blast count) must be assessed within 3 days of the indicated days of each cycle and results reviewed prior to starting dosing if applicable.	X	Days 1, 8, and 22	X	
Coagulation panel	aPTT, INR or prothrombin time (PT) must be assessed at screening and as clinically indicated afterward	X			
Clinical chemistry	At least the following parameters (AST, ALT, sodium, potassium, magnesium, BUN, phosphate, uric acid, calcium, alkaline phosphatase, creatinine, total bilirubin) must be assessed within 3 days of Day 1 of each cycle and results reviewed prior to starting the cycle.	X	X	X	
Assessment for active hepatitis or history of HIV		X			
Serum β -hCG or urine pregnancy test	For women of childbearing potential only	X	Only if clinically indicated		

Procedure (Part B)	Notes	Screening Phase	Open-Label Treatment Phase		Follow-up Phase
		Within 28 days before randomization	Day 1 of each cycle (± 48 hours) unless otherwise indicated (each cycle = 28 days)	EOT	Every 3 months (±7 days)
Disease Evaluations: A +/- 7-day window exists for completion of disease evaluation visits. Refer to Section 9.2 for details on efficacy evaluations					

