5. TREATMENT ALLOCATION AND BLINDING

Treatment Allocation

Procedures for Randomization and Stratification

Central randomization will be implemented in this study for Part B using an interactive web response system (IWRS). Subjects will be stratified by baseline ECOG performance status score (0-1 versus 2) and type of AML (de novo versus secondary) and then assigned randomly to 1 of 2 treatment groups based on a computer-generated randomization schedule prepared before the study by or under the supervision of the sponsor.

After Interim Analysis #2, enrollment to the study was closed and therefore the IWRS was closed to randomization of new subjects.

Blinding

As this is an open study, blinding procedures are not applicable.

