6.1.2. Part B

In Part B of the study, subjects will receive study therapy according to the arm to which they are assigned. The start of each cycle is defined as the date of the first dose of decitabine. Cycles may be delayed due to recovery from toxicity or other causes. Study treatment continues until treatment failure, relapse from CR/CRi, unacceptable toxicity, death, or other reasons specified in Section 10.2.

In Arm 1, study therapy Cycle 1 will start with decitabine at a dose of 20 mg/m² IV administered daily for five consecutive days followed by IV treatment with talacotuzumab (at the RP2D) on Days 8 and 22 (\pm 24 hours) of a 28-day cycle. Subsequent cycles of study therapy will follow the same dosing schedule as Cycle 1 as outlined in Table 3.

Table 3: Dosing Schedule for Part B - Arm 1

Study Day	All treatment cycles									
	1	2	3	4	5	6-7	8	9-21	22	23-28
Decitabine (20 mg/m ²)	X	X	X	X	X					
Talacotuzumab (RP2D mg/kg)							X		X	

Subjects assigned to Arm 2 will receive decitabine at a dose of 20 mg/m² IV administered daily for five consecutive days. A Cycle of study therapy will be repeated every 28 days from the first dose of decitabine onwards. The dosing schedule for Arm 2 is outlined in Table 4.

Table 4: Dosing Schedule for Part B - Arm 2

Study Day	All treatment cycles					
	1	2	3	4	5	6-28
Decitabine (20 mg/m ²)	X	X	X	X	X	

Investigators should be aware that for treatment with decitabine as monotherapy or in combination, it is recommended that subjects be treated for a minimum of 4 cycles; however, a complete or partial response may take longer than 4 cycles.

Study treatment is to continue until treatment failure, relapse from CR/CRi, or death, unless discontinued early because of unacceptable toxicity. Subjects in Arm 1 may discontinue 1 of the study treatments (decitabine or talacotuzumab) because of unacceptable toxicity and continue treatment the other agent until treatment failure, relapse from CR/CRi, or death, unless discontinued early because of unacceptable toxicity.

Following Amendment 6, enrollment to the study was closed and subjects receiving talacotuzumab + decitabine should discontinue talacotuzumab treatment and may continue to receive decitabine alone, according to Principal Investigator decision and subject agreement.

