9.1. Study Procedures

9.1.1. Overview

The [Time and Events Schedules: Tables 1A, 1B, 1C, 1D, 2A, and 2B](#) summarize the frequency and timing of efficacy, pharmacokinetic, immunogenicity, pharmacodynamic, biomarker, pharmacogenomic, patient-reported outcomes, and safety measurements applicable to this study. Every effort should be made to keep subjects on the study schedule as planned from Study Day 1. At each visit, study assessments should be completed before study drug administration. All PRO assessments should be conducted/completed before any tests, procedures, or other consultations to prevent influencing subject perceptions but prior to and on the day of the actual study drug administration.

Post-baseline disease evaluations may be conducted ± 7 days from the scheduled visit date, if necessary. At the following visit, the subject should return to the original planned schedule. Additional serum or urine pregnancy tests may be performed, as determined necessary by the investigator or required by local regulation, to establish the absence of pregnancy at any time during the subject's participation in the study.

Medical resource utilization data will be collected. Refer to Section [9.8](#) for details.

Assuming a study duration of 6 cycles, the total blood volume to be collected from each subject will be approximately 336 mLs for subjects participating in Part A, 541 mLs for subjects participating in Part B Arm 1 (decitabine + talacotuzumab) and 387 mLs for subjects participating in Part B Arm 2 (decitabine only). Repeat or unscheduled samples may be taken for safety reasons or for technical issues with the samples.

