9.1.3. Open-Label Treatment Phase

Details of the procedures performed during the Treatment Phase are outlined in the [Time and Events Schedule Tables 1A](#), [1B](#), and [1C](#). For Part A, treatment will start on Day 1 with an IV infusion of talacotuzumab and proceed as described in [Section 6.1](#). Subjects will continue on study and receive open label talacotuzumab in combination with decitabine in Part A until treatment failure, relapse from CR/CRi, unacceptable toxicity, death or other reasons specified in [Section 10.2](#).

For Part B, treatment with study drug should start within 3 days after randomization and continue until treatment failure, relapse from CR/CRi, unacceptable toxicity, death, or other reasons specified in [Section 10.2](#).

All subjects in Part A and Part B will be closely monitored for adverse events, laboratory abnormalities, and disease status. Clinical evaluations and laboratory studies may be repeated more frequently, if clinically indicated. If treatment failure or relapse from CR/CRi occurs, then the subject will complete the End-of-Treatment Visit and enter the Follow-up Phase. Subjects randomized into the decitabine + talacotuzumab arm can discontinue 1 drug (decitabine or talacotuzumab); while continuing treatment with the other drug.

End of Treatment

All subjects should have an End-of-Treatment Visit, unless a subject withdraws consent for study participation or is lost to follow up. The End-of-Treatment Visit is to occur within 30 days (+/- 7 days) after the last dose of study drug. Every effort should be made to conduct the End-of-Treatment Visit before the subject starts subsequent treatment.

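### The SAP baseline ends on the randomization day, but the first scheduled Part B PRO is on the first-dose day, up to 3 days later, and no PRO-specific baseline rule is given

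*SAP*

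**What the plan says.** SAP 5.5 defines baseline once, without exceptions by type of measure: "The last non-missing value collected on or before the day of randomization".

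The protocol fixes when the first Part B PRO is taken:

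- In Time and Events Table 1B, the screening cell is empty for FACT-Leu and EQ-5D-5L. The note on those rows reads "PROs should be performed on Day 1 of each cycle before dosing and before any study tests or procedures are conducted".
- Protocol 6.1.2 states "The start of each cycle is defined as the date of the first dose of decitabine".
- Protocol 9.1.1 asks for PROs "prior to and on the day of the actual study drug administration".
- The Randomization row of Table 1B reads "Within 3 days prior to the first dose", and Protocol 9.1.3 agrees: "treatment with study drug should start within 3 days after randomization".
- The treatment-phase column of Table 1B is headed "Day 1 of each cycle (± 48 hours) unless otherwise indicated".

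On the analysis side, SAP 6.7.2.7 plans descriptive statistics by arm for 9 PRO measures, at baseline and at each later time point. SAP 5.11 covers scoring only. Neither section defines a PRO baseline or says which visit supplies it.

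**The concern.** The baseline rule is anchored to randomization, while the only scheduled pre-treatment PRO is anchored to the first dose. When those two dates differ, which the protocol allows, the rule excludes the score that ought to be the baseline.

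Read literally, the by-arm baseline rows would leave out every subject first dosed after the randomization day who had no PRO by then. Their untreated scores would be presented among the post-baseline results. One pre-dose visit would then be split between two rows according to how quickly treatment started. The number of observations is reported, so a low N at baseline would reveal the problem, but the SAP gives no rule for resolving it.

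Measures with a screening assessment, such as laboratory tests, vital signs and ECOG status, already have a value that meets SAP 5.5. The gap concerns measures first scheduled on Cycle 1 Day 1, such as the PROs.

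**Working it through.** The plan states no figure on this point to reproduce. The check is one of dates.

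**Inputs.** Let g be the first-dose date minus the randomization date. Table 1B and Protocol 9.1.3 allow g = 0, 1, 2 or 3 days. Protocol 6.1.2 and 9.1.1 place the first PRO on the first-dose date, before the dose. SAP 5.5 accepts a value dated on day 0 (randomization) or earlier.

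**Rule as written.** The first scheduled PRO falls on day g, so it counts as baseline only if g ≤ 0, that is, g = 0.

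**If the 48-hour window is allowed for PROs.** The earliest permitted day is g − 2, which reaches day 0 or earlier only if g ≤ 2.

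| g (days) | Scheduled PRO day | Meets SAP 5.5? | Earliest day with the window | Could meet SAP 5.5? |
|---|---|---|---|---|
| 0 | 0 | yes | −2 | yes |
| 1 | 1 | no | −1 | yes, if done early |
| 2 | 2 | no | 0 | yes, if done early |
| 3 | 3 | no | 1 | no |

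**Share affected.** Let s be the share of dosed subjects whose first dose is on the randomization day. The share with no PRO scheduled on or before the cutoff is 1 − s. The documents do not give s, so the bounds are 1 − 1 = 0% and 1 − 0 = 100%. For illustration only, under assumed values of s:

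- s = 0.80 gives 1 − 0.80 = 20%.
- s = 0.50 gives 1 − 0.50 = 50%.
- First doses spread evenly over the 4 permitted calendar days give s = 1/4, so 1 − 0.25 = 75%.

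**After the fix.** If baseline is the last assessment before the first dose, the Cycle 1 Day 1 pre-dose score qualifies at every g from 0 to 3.

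**The case against.** The case on the other side has four parts.

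1. **The effect is mainly one of labelling.** Protocol 11.10 has PRO scores summarized at each time point, so a Cycle 1 Day 1 score that misses the baseline row would still be reported by arm elsewhere. No PRO change from baseline, model or test depends on it. This stands, and it is why the point is minor. What remains is a baseline row with missing subjects and untreated scores under a post-baseline label.

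2. **The intended baseline is evident.** SAP 5.3 describes the Screening Phase as the time before first dose, which makes a pre-dose score a pre-treatment value, and an analyst would probably use Cycle 1 Day 1. That is a sensible reading of intent. However, SAP 5.3 starts the Treatment Phase on the date of first dose, so by date alone the same score falls there. The section defines phases and does not amend SAP 5.5. Using Cycle 1 Day 1 would depart from the written rule.

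3. **The 48-hour window may cover it.** The PRO row restricts the order of events more clearly than the date, and only Protocol 9.1.1 ties PROs to the dosing day. If the window applied, it could partly close the gap at 1 or 2 days. But it yields where something else is indicated, and Protocol 9.1.1 does so for PROs. It would also only permit early completion, not require it, and it would still miss a 3-day gap.

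4. **The size is unknown.** This is correct. The percentages shown are assumptions, not estimates.

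**Conclusion.** The point holds, as a minor one. Followed exactly, SAP 5.5 leaves subjects first dosed 1 to 3 days after randomization without a scheduled PRO baseline, and nothing else in the SAP repairs this. A PRO that happened to be completed on or before the randomization day would still count, and subjects dosed on that day are unaffected.

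The conclusion rests on reading Protocol 9.1.1 as placing PROs on the dosing day. If the 48-hour window were held to apply instead, only a 3-day gap would necessarily miss the cutoff. The share affected cannot be estimated from the documents. The consequence is confined to the descriptive PRO summaries of a secondary endpoint.

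**What to change.** Add to SAP 5.5 or 5.11: for FACT-Leu and EQ-5D-5L, baseline is the last non-missing assessment before the first dose of study drug, including the Cycle 1 Day 1 pre-dose assessment; subjects who were never dosed and have no PRO are counted as missing baseline. The general rule can stay as it is for other measures. Anchoring to the first dose matches how the SAP already defines study phases (5.3), prior medication (5.8) and treatment-emergent events (5.15).

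Add a footnote to the PRO table giving the number of baselines collected after the randomization day. Protocol Section 5 states "As this is an open study, blinding procedures are not applicable", so a subject may know the allocation when completing a baseline after randomization. The footnote is a transparency measure and is separate from the date conflict.

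The cost is two sentences and one footnote, with no new data collection.

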5.6. Major Protocol Deviation

Major protocol deviations to be identified by the Sponsor prior to database lock are:

- Study entry criteria not met
- Received prohibited concomitant medication
- Study drug treatment deviation or crossover

5.7. Cytogenetic Risk

Cytogenetic risk (favorable, intermediate-I, intermediate-II, or adverse) will be determined by the Sponsor using collected cytogenetic data according to the criteria for AML diagnosis and management by European LeukemiaNet¹.

5.8. Prior and Concomitant Medications

Medications administered prior to the first dose of study medication are considered prior medications. Concomitant therapies include those taken on or after first dose through 30 days after the last dose.

5.9. Disease Status per Central Review and Investigator’s Assessment

Disease status (including response) based on central review by the IRC will be the primary source for all pertinent analyses. Analyses based on investigator’s assessment will also be performed. Any major discordance between the 2 assessments affecting interpretation of study outcomes may be investigated.

5.10. MRD Negativity

For subjects who achieved CR or CRi, a bone marrow sample will be taken and MRD status will be determined by flow cytometry. The leukemia-associated immunophenotype (LAIP) will be determined upon diagnosis, and will be tracked in each subject during treatment. If applicable, multiple LAIPs will be identified and tracked over time. MRD negativity will be defined as having less than 1 leukemic blast from an identified LAIP in 10,000 leukocytes.

Upon early termination of study recruitment after the second interim analysis, MRD assessments are no longer performed.

5.11. Patient-Reported Outcomes

5.11.1. FACT-Leu

The FACT-Leu is a 44-item² self-reported measure used to quantitatively assess individuals' perception of how the disease affects their daily life. It includes 5 subscales, ie, physical well-being (PWB), social/family well-being (SWB), emotional well-being (EWB), functional well-being (FWB), and leukemia-specific concerns (LeuS). All FACT-Leu subscales and aggregated scores showed high internal consistency and high test-retested reliability.

The FACT-G is considered appropriate for use with subjects with any form of cancer, and has also been used and validated in other chronic illness conditions. The additional items of the FACT-Leu and LeuS allow for constructing a leukemia subscale. The subject is asked to rate the scale items as it applies to the past 7 days, on a 5-point scale (0=not at all, 1=a little bit, 2=somewhat, 3=quite a bit, 4=very much). Negatively stated items will be reversed by subtracting the response from 4. After reversing the proper items, items are summed to a total to generate a score on a (sub) scale^{3,4}.

- FACT-Leu trial outcome index (TOI) = PWB + FWB + LeuS
- FACT-G total score = PWB + SWB + EWB + FWB
- FACT-Leu total score = PWB + SWB + EWB + FWB + LeuS

5.11.2. EQ-5D-5L

The EQ-5D-5L is a generic measure of health status. For purposes of this study, the EQ-5D-5L will be used to generate utility scores for use in cost effectiveness analyses. The EQ-5D-5L is a 5-item questionnaire that assesses 5 domains including mobility, self-care, usual activities, pain/discomfort and anxiety/depression, plus a VAS rating "health today" with anchors ranging from 0 (worst imaginable health state) to 100 (best imaginable health state)^{5,6}. The scores for the 5 separate questions are categorical and cannot be analyzed as cardinal numbers. As such, the EQ-5D Health Utility Index (HUI) will also be generated. The HUI is calculated from scores of the five health state domains and is scored between -1 (worst imaginable health state) and 1 (best imaginable health state), with 0 representing a health state equivalent to death. The United Kingdom weights will be used to generate patient utilities from the 5 dimensions of the EQ-5D-5L in this study.

5.12. Interim Analyses

All interim analyses will be conducted by an external independent statistical group and reviewed by the IDMC. The IDMC procedures and interim analysis details are described in a separate IDMC charter and a statistical analysis plan, respectively.

5.13. Subgroups

Selected efficacy analyses will be performed for the following subgroups:

- Age (<75, ≥75 years)
- Gender (male, female)
- Region (North American, Western Europe, rest of world)
- Type of AML (de novo, secondary)
- Cytogenetic risk (adverse, other)
- Baseline ECOG performance status (0-1, 2)
- Bone marrow blasts (≤50%, >50%)
- Platelet (≤60, >60, 10⁹/L)
- WBC (≤4, >4, 10⁹/L)

5.14. Dose Intensity

The unit for dose intensity calculation will be mg/m²/cycle for decitabine and mg/kg/cycle for talacotuzumab. Relative dose intensity is calculated as percent of intensity of received dose versus prescribed dose.

5.15. Treatment-Emergent Adverse Events

Treatment-emergent AEs are defined as those that occurred after the first dose of study drug through the last dose date + 30 days or the start of a subsequent anticancer therapy, whichever occurs earlier. Adverse events that occurred any time after the first dose of study drug during the study are also considered as treatment-emergent if they are study drug-related (ie, possible, probable, or very likely related to study drug).

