Abbreviations: AE=adverse event; ALT= alanine aminotransferase; AML=acute myeloid leukemia; ANC= absolute neutrophil count; AST= aspartate aminotransferase; β -hCG=beta human chorionic gonadotropin; CCO=clinical cut-off; CR= complete response; CRi= complete response with incomplete blood count recovery; BP=blood pressure; BUN= blood urea nitrogen; ECG=electrocardiogram; ECOG=Eastern Cooperative Oncology Group; EOT=end of treatment; EQ=EuroQol; HBV: hepatitis B virus; HR=heart rate; ICF=informed consent form; INR= international normalized ratio; LDH= lactate dehydrogenase; LVEF= left ventricular ejection fraction; MRD= minimal residual disease; MUGA= multi gated acquisition scan; NK= natural killer (cells); PD=pharmacodynamics(s); PK=pharmacokinetic(s); PT= prothrombin time; aPTT= partial thromboplastin time; SAE=serious adverse event; T&E=Time & Events; WBC= white blood cell.					

TIME AND EVENTS SCHEDULE – TABLE 1C [PART B] DURING AMENDMENT 6

Procedure (Part B)	Notes	Screening Phase	Open-Label Treatment Phase		Follow-up Phase
		Within 28 days before randomization	Day 1 of each cycle (\pm 48 hours) unless otherwise indicated (each cycle = 28 days)	EOT	Every 2 months (\pm 7 days)
NOTE Following Amendment 6, which incorporated the IDMC's recommendations to close enrollment to the study and discontinue talacotuzumab treatment for subjects receiving talacotuzumab + decitabine and offer to continue decitabine alone, all subjects will continue to be followed for survival and subsequent anti-cancer therapy. During the treatment phase with decitabine, subjects will be monitored for serious adverse events.					
Serious adverse events	Follow until resolution		X		
Survival, subsequent therapy			X	X	X
EOT= end-of-Treatment; IDMC= Independent Data Monitoring Committee					

TIME AND EVENTS SCHEDULE – TABLE 1D [PART B] FOLLOWING AMENDMENT 7

Procedure (Part B)	
NOTE Following Amendment 7 and when 270 deaths have occurred or 6 months after the last subject is enrolled (whichever occurs first), follow up of subjects and data collection will end. Subjects who are continuing to derive benefit from decitabine treatment as assessed by their investigator may continue to receive decitabine; during this period, only serious adverse events will be monitored and entered into the Company safety repository.	

TIME AND EVENTS SCHEDULE (PK AND BIOMARKERS) – TABLE 2A [PART A]

PART A	Cycle 1						Cycle 2	Cycles 3 and 5	EOT ¹
	Talacotuzumab alone						Decitabine + Talacotuzumab		

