11.11. Safety Analyses

Adverse Events

The verbatim terms used in the eCRF by investigators to identify adverse events will be coded using the Medical Dictionary for Regulatory Activities (MedDRA). Toxicities will be graded for severity according to NCI-CTCAE, version 4.03. All reported adverse events with onset during the treatment phase (ie, treatment-emergent adverse events, and adverse events that have worsened since baseline) will be included in the analysis. For each adverse event, the percentage of subjects who experience at least 1 occurrence of the given event will be summarized by treatment group.

Specifically, the following will be summarized:

- All adverse events;
- Grade 3 or higher adverse events;
- Serious adverse events;
- Adverse events leading to discontinuation of treatment;
- Adverse events leading to death; and
- Adverse events of special interest.

Summaries, listings, datasets, or subject narratives may be provided, as appropriate, for those subjects who die, who discontinue treatment due to an adverse event, or who experience a severe or a serious adverse event.

Clinical Laboratory Tests

Laboratory data will be summarized by type of laboratory test. Reference ranges and markedly abnormal results (specified in the Statistical Analysis Plan) will be used in the summary of laboratory data. Descriptive statistics will be calculated for each laboratory analyte at baseline. Parameters with predefined National Cancer Institute Common Terminology Criteria for Adverse Events (NCI-CTCAE) toxicity grades will be summarized. Change from baseline to the worst adverse event grade experienced by the subject during the study will be provided as shift tables.

Electrocardiogram (ECG)

Electrocardiogram data will be presented by descriptive analysis only.

Vital Signs

Descriptive statistics of heart rate and supine blood pressure (systolic and diastolic) values and changes from baseline will be summarized. The percentage of subjects with clinically important changes from baseline will be summarized.

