12.1. Definitions

12.1.1. Adverse Event Definitions and Classifications

Adverse Event

An adverse event is any untoward medical occurrence in a clinical study subject administered a medicinal (investigational or non-investigational) product. An adverse event does not necessarily have a causal relationship with the treatment. An adverse event can therefore be any unfavorable and unintended sign (including an abnormal finding), symptom, or disease temporally associated with the use of a medicinal (investigational or non-investigational) product, whether or not related to that medicinal (investigational or non-investigational) product (Definition per International Conference on Harmonisation [ICH]). This includes any occurrence that is new in onset or aggravated in severity or frequency from the baseline condition, or abnormal results of diagnostic procedures, including laboratory test abnormalities. Note: The sponsor collects adverse events starting with the signing of the ICF (refer to Section 12.3.1, All Adverse Events, for time of last adverse event recording).

Serious Adverse Event

A serious adverse event based on ICH and EU Guidelines on Pharmacovigilance for Medicinal Products for Human Use is any untoward medical occurrence that at any dose:

- Results in death

- Is life-threatening
(The subject was at risk of death at the time of the event. It does not refer to an event that hypothetically might have caused death if it were more severe.)
- Requires inpatient hospitalization or prolongation of existing hospitalization
- Results in persistent or significant disability/incapacity
- Is a congenital anomaly/birth defect
- Is a suspected transmission of any infectious agent via a medicinal product
- Is Medically Important*

*Medical and scientific judgment should be exercised in deciding whether expedited reporting is also appropriate in other situations, such as important medical events that may not be immediately life threatening or result in death or hospitalization but may jeopardize the subject or may require intervention to prevent one of the other outcomes listed in the definition above. These should usually be considered serious.

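### The SAP's treatment-emergent AE definition has no clause for pre-dose events that worsen on treatment, although the protocol's safety analysis includes them

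*SAP*

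**What the plan says.** SAP 5.15 gives the rule: "Treatment-emergent AEs are defined as those that occurred after the first dose of study drug through the last dose date + 30 days". The window closes sooner if another anticancer treatment begins before then. A second sentence extends the window for related events: AEs at any later time in the study "are also considered as treatment-emergent if they are study drug-related". That sentence also requires the event to have occurred after the first dose. SAP 6.8.1 builds its incidence tables on this definition and asks for the same summary for serious AEs, AEs leading to discontinuation and AEs leading to death.

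Protocol 11.11 describes the set for analysis as "treatment-emergent adverse events, and adverse events that have worsened since baseline". Protocol 12.1.1 defines an AE to include "any occurrence that is new in onset or aggravated in severity or frequency from the baseline condition", and 12.3.1 starts AE recording at signed consent.

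On collection after enrolment closed, Table 1C and the opening of Protocol 12.3 state: "During the treatment phase with decitabine, subjects will be monitored for serious adverse events". Protocol 9.9 and 12.3.1 still have AEs reported until 30 days after the last dose, and 12.3.1 names serious and non-serious events alike.

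**The concern.** The protocol leaves statistical detail to the SAP, but dropping a class of events that the protocol names is more than detail, and the SAP gives no reason for it. Pre-dose AE records will exist. Part B screening runs up to 28 days before randomization and dosing should start within 3 days after it. An AE can therefore start up to about 28 + 3 = 31 days before the first dose if consent is signed at the start of the screening window. At stake is whether an event such as an infection or bleed that begins in that period and becomes more severe on treatment reaches the treatment-emergent tables. Infection, bleeding and febrile neutropenia are all AEs of special interest in SAP 5.16.

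A second question concerns the end of the window. SAP 5.15 uses one window for serious and non-serious events, and SAP 3 analyses data to 6 months after the last randomization, which takes in the Amendment 6 period. The SAP adjusts for the end of central response review (5.2) and of MRD assessment (5.10), but is silent on whether AE collection changed.

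**Working it through.** No figure in the plan bears on this point, so the check is a comparison of the rules case by case.

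| Case | Protocol 11.11 | SAP 5.15 |
|---|---|---|
| AE starts after the first dose | counted | counted |
| AE starts before the first dose; worsening entered as a new AE after dosing | counted | counted |
| AE starts before the first dose; grade raised on the same record after dosing | counted | **not counted** |
| AE starts in screening and does not worsen | not counted | not counted |

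The rules differ only in the third case. The related-event sentence in SAP 5.15 does not rescue it, because the event still has to have occurred after the first dose.

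For one AE category, the incidence lost is p × q × r × s, where:
- p is the share of subjects with a pre-dose AE record in that category;
- q is the share of those whose event worsens after dosing;
- r is the share of worsenings regraded on the same record;
- s is the share of those subjects with no other treatment-emergent event in the category.

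The documents give none of the four, so no estimate follows. If r = 0, the loss is zero. The direction is fixed: the added clause can bring subjects into a table and cannot remove any.

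On the collection window, the passages compare as follows:
- The schedule row for all AEs is in Table 1B, which applies up to and including Amendment 5.
- Table 1C, for Amendment 6, lists serious AEs, survival and subsequent therapy, with no row for non-serious AEs. The opening of Protocol 12.3 agrees with it.
- Protocol 9.9 and 12.3.1 keep the full period to 30 days after the last dose, which matches SAP 5.15. Section 12.3.1 sits under the 12.3 text it conflicts with.
- The explicit restriction to serious AEs only belongs to Amendment 7. It starts when data collection ends, so it does not settle the Amendment 6 period.

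The conflict matters only for subjects still on treatment, or within 30 days of their last dose, when Amendment 6 took effect.

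**The case against.** The strongest reply is that the AE definition already does the work. An aggravation is itself an AE under Protocol 12.1.1, so an aggravation after the first dose is an AE that occurred after the first dose. Protocol 9.9 also requires clinically relevant changes to be entered in the AE section of the eCRF. This largely stands and confines the gap to same-record regrading. It does not close it, because neither document tells sites to open a new record when a grade changes.

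A reader might infer that worsening events, even to Grade 4 or 5, vanish from the safety report. The documents do not support that. SAP 6.8.2 tabulates shifts to worst grade for selected hematology and chemistry parameters, and SAP 6.8.1 summarizes all deaths on study with cause. An unresolved infection that helps a subject qualify is a baseline condition, so its aggravation is a new AE. It is a qualifying condition only in the 65-to-75 group, and exclusion 6.1 removes uncontrolled systemic infection needing IV antibiotics.

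A reader might also put a number on the loss. Setting p and q at 10% to 30% gives 0.10 × 0.10 = 1 to 0.30 × 0.30 = 9 percentage points. Those inputs are assumptions with no source in the documents, and the product takes r = s = 1, the least favourable values.

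Finally, a reader might infer that non-serious collection stopped at Amendment 6 and that the window should end there. The protocol says both things. The SAP 6.8.1 tables count subjects with an event, so uncollected time does not inflate a denominator as it could for the transfusion rate in SAP 6.7.3. Cutting the window could discard non-serious AEs validly reported under Protocol 9.9 and 12.3.1.

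**Conclusion.** The point holds in a limited form. The SAP's written rule omits a class of AEs that Protocol 11.11 includes. The omission takes effect only where an event that began before dosing was regraded on its existing record; outside the laboratory shift tables and the death summary, that worsening would not be shown as treatment-emergent. Its size cannot be derived from the documents and depends on eCRF practice, which they do not describe. Efficacy conclusions are unaffected.

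The Amendment 6 question is an unresolved conflict within the protocol and does not show an error in the SAP's window. The documents support reconciling the passages and stating what was collected.

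**What to change.** Add to SAP 5.15: *or that started before the first dose and worsened in grade on or after it, within the same window*. State in the same place whether a grade change opens a new AE record or updates the existing one. The cost is one clause and a comparison of the last pre-dose grade with the worst grade in the window. That comparison needs grade changes to be dated on the record. If sites always opened new records, the tables do not change; otherwise reported incidence may rise slightly.

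Separately, reconcile Table 1C and Protocol 12.3 with Protocol 9.9 and 12.3.1, and record in the SAP which AEs were collected under Amendment 6. If non-serious collection did stop, keep the window and label the all-grade tables to say that non-serious AEs are complete only up to Amendment 6. That costs a sentence and a footnote.
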